4.2. Key Definitions

The following key definitions will be used:

• Study Day: Within each treatment cycle, the study day of an event is defined as the relative day of the event starting with the date the study drug administration (reference date) for that Cycle as Study Day 1 (there will be no Day 0 for analysis purposes). The study day of events occurring before the first study drug administration in the first treatment cycle will be calculated as:

Study Day = (date of event – date of first study drug administration).

For events occurring on or after Study Day 1 in the first treatment cycle (including protocol specified Day 0 "rollover" visit), study day will be calculated within cycles as:

Study Day = (date of event/visit within a cycle – Date of study drug administration of that cycle) + 1.

Study days will only be calculated for events with complete or imputed dates and will be undefined for events that are "ongoing" at the end of the study.

- Baseline: The last observation on or before date of first dose in the ABP-19000 study will be considered as the baseline measurement unless otherwise specified. Repeat or unscheduled assessments may be included in the derivation of the baseline value.
- Change from baseline: The change from baseline value is defined as the difference between the result collected/derived at a post-baseline visit/timepoint within a cycle and the baseline value. The change from baseline value at each post-baseline visit/timepoint within a Cycle will be calculated for all continuous parameters using the formula:

Change from baseline Value = Result at Visit or Timepoint within a cycle– Baseline Value

The change from baseline value will only be calculated if the specific post-baseline visit/timepoint within a treatment cycle results and the baseline value for the parameter are both available and will be treated as missing otherwise.

All analyses will be conducted using

4.3. Sample Size

All eligible patients who had their initial dose of study drug in the ABP-19000 study, irrespective of treatment allocation, and consented to being treated with ABP-450 can be enrolled in this OLE (i.e., ABP-19002) study.

Approximately 59 patients could enroll in this OLE study from the ABP-19000 study. As there will be no comparative analyses, study power and sample size justifications are not required.

4.4. Randomization, Stratification, and Blinding

This is an OLE study. All eligible patients from the ABP-19002 study will receive ABP-450 in an unblinded fashion. As the blind will not be broken, the placebo patients (who were entered into

one of the dose groups in the ABP-19000 study) can be administered any dose between 150 and 350 units of ABP-450, based on the investigator's discretion.

4.5. Analysis Set

The following analysis sets will be used for this study. Inclusion in each analysis set will be reviewed and confirmed prior to database lock. The number and percent of patients in each analysis set will be summarized. A listing will also be produced displaying patients excluded from each set.

4.5.1. Enrolled Set

Enrolled Set will include every patient who signed informed consent form and attended Visit. The Enrolled Set will only be used for summaries of patient disposition and protocol deviations.

4.5.2. Modified Full Analysis Set (mFAS)

The mFAS will consist of all patients in the Safety Analysis Set but will exclude patients

The mFAS will be used for analysis of

secondary estimands.

4.5.3. Safety Analysis Set (SAF)

The SAF will consist of all patients who received at least one dose of the investigational study drug. The SAF will be used to tabulate all safety data excluding the primary estimand.

4.5.4. Safety Analysis Set with Retreatment (SAFR)

The SAFR will consist of all patients in the SAF but will exclude patients who do not receive more than one treatment of ABP-450 within the OLE study. The SAFR will be used for analysis of the primary estimand.

5. Patient Disposition

5.1. Disposition

Patient disposition will be summarized by overall treatment group and presented in a listing for patients in the Enrolled Set. The disposition of patients will include the number and percentage of patients for the following categories:

- Patients enrolled.
- Patients included in the mFAS.
- Patients included in the SAF.
- Patients included in the SAFR.
- Patients who discontinued treatment with corresponding reasons for treatment discontinuation.
- Patient included in the SAF with corresponding reasons for treatment discontinuation.
- Patients who withdrew from the study with corresponding reasons for study withdrawal.

The reasons for discontinuation of ABP-450 treatment or withdrawal from the study include:

• Adverse Event

- Death
- Lack of Efficacy
- Lost to Follow-up
- Non-Compliance with Study Drug
- Physician Decision
- Pregnancy
- Study Terminated by Sponsor
- Withdrawal by Subject
- Other

5.2. Protocol Deviations

A listing of patients with protocol deviations will be provided.

6. Demographics and Baseline Characteristics

Demographic and baseline information will be summarized descriptively by overall treatment group (low, medium, high) as described in Section 4.1 using the mFAS and SAF and presented in listings using SAF.

6.1. Demographics

The following demographic parameters will be summarized:

Continuous descriptive analysis

- Age (years, as collected on the eCRF)
- Height (cm)
- Weight (kg)
- Body Mass Index (BMI) (kg/m²). The BMI will be calculated as (body weight in kilograms) / (height in meters)².

Categorical descriptive analysis

- Sex (Male, Female)
- Ethnicity (Hispanic or Latino, Not Hispanic or Latino, and Not Reported)
- Race (White, Black or African American, Asian, American Indian or Alaska Native, Native Hawaiian or Other Pacific Islander, Other, and Not Reported)

6.2. General Medical History

Medical history and current medical conditions will be coded using the ICH Medical Dictionary for Regulatory Activities (MedDRA) version 25.0 or later. Relevant prior medical history and current medical conditions will be summarized by overall treatment group (low, medium, high) system organ class (SOC) and preferred term (PT), using the SAF. Summary tables will include the number and proportion of patients (%) experiencing an event. Patients will be counted once for each SOC and PT level. General medical history data will also be listed using the SAF.

6.3. Inclusion and Exclusion Criteria

Inclusion and exclusion criteria not met by patients will be listed using the Enrolled Set. Inclusion criteria and exclusion criteria may be found in Protocol Sections 4.1.1 and 4.1.2, respectively.

7. Treatments and Medications

7.1. Prior and Concomitant Medications

Prior and concomitant medications will be documented and updated during the study. Prior and concomitant medications will be coded according to the latest World Health Organization drug dictionary (WHODRUG Sep 2022 or later).

Medications that started prior to and continued after the first dose of ABP-450 will be included as both prior and concomitant medications. Summaries of prior and concomitant medications will be presented by overall treatment group (low, medium, high), PT and based on the SAF.

7.1.1. Prior Medications

A prior medication is defined as any medication that is taken prior to the first dose of ABP-450 regardless of when they stopped. If start and stop dates are missing and the medication is not identified to be ongoing, the medication will be considered 'prior medications' if the data was entered at Visit 1 (Baseline). Prior medications will be tabulated and listed. Medications that were started during and prior to the ABP-19000 study will be flagged in the listings.

7.1.2. Concomitant Medications

A concomitant medication is defined as any medication (other than ABP-450) that was used at least once on or after the date of first dose of ABP-450. Medications that were stopped on the same date as the first dose of ABP-450 will be included as concomitant medications. All medications which are ongoing will be considered concomitant. In addition, if a clear determination cannot be made (e.g., missing or partial medication start and/ or end dates), the medication will be included as concomitant.

7.2. Study Treatments

7.2.1. Extent of Exposure to ABP-450

The number and percentage of patients exposed to study treatment at each visit within each treatment cycle will be summarized descriptively for categorical parameters by treatment group, while the cumulative number of doses and cumulative dose at each visit within each treatment cycle and total ABP-450 administered overall will be summarized descriptively for continuous parameters as described in Section 4.1, using the SAF.

7.2.2. Treatment Compliance

ABP-450 will be administered to the patient at the trial site by trained trial staff. Precise dose administered, the time and date of dosing in the source document and the dosage administration will be recorded in the eCRF. No analysis of compliance is planned for ABP-450.

8. Safety Analysis

8.1. Adverse Events

AEs will be collected from the time of signing of the ICF until 52 weeks or end of treatment after Day 1 "rollover" (exit from the study). All AEs will be classified by SOC and PT according to the MedDRA, version 24.0 or later.

Serious AEs that occur more than 56 days (i.e., 8 weeks) after the last dose of investigational study drug and the patient has exited the study may be reported if the investigator considers them related to investigational study drug.

[figure not shown]
The severity or intensity of an AE refers to the extent to which an AE affects the patient's daily activities. Adverse event severity will be classified as "Mild", "Moderate", and "Severe". TEAEs with missing severity will be imputed as 'Severe'.

The investigator will provide an assessment of the relationship of the event to the trial drug. The possible relationships are "Unrelated", "Possibly Related", "Probably Related" and "Definitely Related". Any TEAE reported as "Definitely Related", "Possibly Related" or "Probably Related" will be considered related to the ABP-450. TEAEs that are missing a relationship will be counted in the summary table as "Definitely Related" but will be presented in the data listing with a missing relationship.

Treatment emergent adverse events (TEAEs) are defined as those AEs that started on or after the day of first dose of ABP-450 up to 5 days after the end of treatment or end of study visits. Only TEAEs will be included in the AE summary tables. However, all adverse events will be listed and TEAEs will be flagged.

[figure not shown]
The TEAEs will be summarized by SOC and PT and will include the number and percentage of patients experiencing an event and the number of events (based on start date of the event) by treatment cycle and treatment group. Patients will be counted only once for each SOC and PT level (categorical descriptive analyses). In general, TEAE summary tables will be sorted by SOC and PT in descending order of frequency from the SOC and PT with the highest total frequency to the SOC and PT with the lowest total frequency.

For the purpose of inclusion in TEAE tables, incomplete AE onset and end dates will be imputed following date imputation guidelines (see Section 13.2).

[figure not shown]

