6.2.1 Adverse Events

6.2.1.1 Definitions of Adverse Events

The investigator is responsible for reporting all AEs that are observed or reported during the study, regardless of their relationship to investigational study drug. The investigator will query the patient for changes since last visit and ask about the patient's ability to swallow.

An AE is defined as any untoward medical occurrence in a patient enrolled into this study regardless of its causal relationship to investigational study drug. Patients will be instructed to contact the investigator at any time after enrollment if any symptoms develop.

A treatment-emergent AE is defined as any event not present before exposure to investigational study drug or any event already present that worsens in either intensity or frequency after exposure to investigational study drug.

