8.1.4. Relationship of Adverse Events to Study Drug

Summaries of TEAEs related to ABP-450 will be presented by SOC and PT in descending order of frequency by treatment group within each treatment cycle. Summaries for TEAEs related to

ABP-450 will be presented using patients in the SAF who received at least one dose of ABP-450. Data will be listed for the SAF.

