8.1.6. Serious Adverse Events

Treatment-emergent SAEs will be presented by SOC and PT in a manner similar to that described in Section 8.1. Incidence and frequency summaries and listings of all treatment-emergent SAEs will be presented for the SAF by treatment group in each treatment cycle, and across all cycles (by overall total doses of low, medium, and high).

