8.1.9. Suspected Unexpected Serious Adverse Events

A suspected unexpected serious adverse event (SUSAR) is defined as an AE, the nature or severity of which is not consistent with the applicable product information (e.g., investigator's brochure for an unapproved investigational medicinal product). The incidence of SUSARs will be summarized by SOC, PT, and treatment group for each treatment cycle.

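### SAP 8.1 defines treatment-emergent AEs by start date alone and omits the protocol's worsening clause, so an AE that starts before the first open-label dose and worsens afterwards on the same record is listed but not tabulated

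*SAP*

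**What the plan says.** SAP 8.1 defines TEAEs as "those AEs that started on or after the day of first dose of ABP-450", ending "up to 5 days after the end of treatment or end of study visits. Only TEAEs will be included in the AE summary tables". It has no clause for worsening. Everything else goes to the listings: "However, all adverse events will be listed and TEAEs will be flagged".

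Protocol 6.2.1.1 counts an event that was absent before exposure and also "any event already present that worsens in either intensity or frequency after exposure to investigational study drug". It sets no end date.

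The narrower SAP sections follow the SAP 8.1 rule. For related events (8.1.4), "Summaries of TEAEs related to ABP-450 will be presented by SOC and PT in descending order of frequency". For serious events (8.1.6), "Incidence and frequency summaries and listings of all treatment-emergent SAEs will be presented for the SAF". The SUSAR section (8.1.9) does not repeat the restriction, "The incidence of SUSARs will be summarized by SOC, PT, and treatment group for each treatment cycle", but the general rule in 8.1 covers it.

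On late events, Protocol 6.2.1.2 releases sites from reporting SAEs that occur more than 56 days after the last dose in patients who have left the study, except those the investigator considers related. SAP 8.1 says that such related SAEs "may be reported if the investigator considers them related to investigational study drug".

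**The concern.** Safety is the primary objective, and readers of the study report will rely mainly on the TEAE tables. If the SAP applies a narrower definition than the protocol, the tables do not show what the protocol calls treatment-emergent. The events at risk are those for which the worsening clause exists: something already present and mild that becomes moderate or severe after an injection.

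A second, smaller matter concerns the end of the window. Both documents foresee related SAEs after a patient has left the study, yet the visible SAP text gives an SAE with onset after the window no row in any summary table.

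**Working it through.** **Worsening clause.** No figure in the plan is at issue, so the check is to run the possible cases through both definitions. First dose is read here as the first open-label dose, because SAP 4.2 names ABP-19000 where it means the parent-study dose.

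| Case | Protocol 6.2.1.1 | SAP 8.1 |
|---|---|---|
| AE starts on the dosing day or later, within the window | Treatment-emergent if not present before exposure | TEAE, tabulated |
| Pre-existing condition deteriorates after dosing; AE onset entered as the date of deterioration | Treatment-emergent | TEAE, tabulated |
| Same, but AE onset entered as the date the condition first appeared | Treatment-emergent | Listed only |
| AE starts between consent and first open-label dose, then worsens; change entered on the same record | Treatment-emergent | Listed only |

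The definitions disagree in the last two rows. Whether the third arises depends on an onset-date convention that Protocol 6.2.1.4 does not give. The fourth fits the recording rules: Protocol 6.2.1.7 and SAP 8.1.5 have severity changes captured within an AE, and SAP 8.1 counts events by start date. For worsening in frequency, Protocol 6.2.1.7 does not require each episode of an intermittent AE to be dated, so a new start date may never be created.

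If first dose instead meant the first ABP-450 dose in either study, the fourth row would remain only for patients who had placebo in the parent study.

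**End of window.** Inputs: last permitted retreatment at Week 48 (Protocol 3.1), end-of-study visit 52 weeks after Day 0 (Protocol 11.3), the 5 days of SAP 8.1, and the 56 days of Protocol 6.2.1.2. Days are counted from Day 0, with the final visit assumed to fall exactly at Week 52.

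- Latest dose: 48 × 7 = day 336.
- Window closes: 52 × 7 + 5 = day 369.
- Reporting cut-off after that dose: 336 + 56 = day 392.
- Difference: 392 − 369 = 23 days.

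For a last dose on day L the difference is max(0, L + 56 − 369). This gives 16 days for Week 47, 9 for Week 46, 2 for Week 45 and 0 for Week 44 or any L up to day 313. For an early leaver seen d days after the last dose, if that visit closes the window, it is max(0, 56 − (d + 5)) = max(0, 51 − d): 37 days at d = 14, 23 at d = 28, 9 at d = 42.

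The 56 days is a reporting cut-off, not a tabulation period. The protocol implies, without saying so, that SAEs inside it stay reportable after exit. The differences therefore show distance to the cut-off and are not a measure of lost events.

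**The case against.** The best reply on the worsening clause is that Protocol 6.2.1.4 almost closes the gap. A stable pre-existing condition is not reported as an AE at all. It becomes one on deterioration, so there will often be no record with a pre-dose start date. AEs starting on the dosing day already count, and the visible text gives no length for the interval from consent to first open-label dose. This stands as a reason to call the gap narrow. It does not close it, because no onset-date rule is given and severity changes stay within the existing record.

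On the end of the window, a reader might infer that the SAP contradicts the protocol. The documents do not support that. Protocol 6.2.1.1 sets no end date, Protocol section 7 leaves analysis definitions to the SAP, and both documents end routine AE collection at exit, so the window covers planned collection plus 5 days. Nor does the missing worsening clause cause the late-SAE result; that comes from the closing date alone. The rule turns on onset, so an SAE that starts inside the window and is reported late is still a TEAE.

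A reader might also infer that late SAEs certainly reach no table. Parts of SAP 8.1 to 8.1.2 and the content of SAP section 11 are not visible, and a rule or a declared departure could sit there. Only the visible text can be judged.

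Finally, safety oversight does not depend on these tables: Protocol 6.2.1.5 covers expedited SAE reporting and Protocol 6.4 provides monthly review of all AEs. That limits the consequence to how the results are presented.

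**Conclusion.** The definitional difference is real and rests on complete, visible sentences: the protocol counts worsening of an existing event and the SAP does not. Its effect is confined to AEs whose recorded start date precedes the first open-label dose and which worsen afterwards on the same record. The documents do not show how many patients that involves.

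No direction of bias is claimed, because other rules in SAP 8.1 raise counts: missing severity is set to severe, missing causality is counted as definitely related, and any AE starting on the dosing day is included. A reader might infer that the primary analysis is affected. That is not supported: Protocol 7.5.1 stops at Week 52 (day 364), before the window closes on day 369 for completers, and the text of SAP 8.1.1 is not visible.

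The handling of post-window SAEs is a secondary point and an opportunity for clearer reporting. These events stay in the AE listing and, if fatal, the death listing.

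**What to change.** In SAP 8.1, define a TEAE as an AE that starts, or worsens in intensity or frequency, on or after the day of the first open-label dose, within the current window. Say that the date of worsening replaces the start date when such an event is assigned to a treatment cycle and dose group, since the tables otherwise count by start date. State which onset date applies when a pre-existing condition deteriorates.

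As a secondary change, add one summary table of SAEs with onset after the window, including later ones considered related, kept apart from the TEAE tables and footnoted as passively reported. It is not needed if redacted text already provides it.

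The cost is SAP wording, minor programming and one table, with no new visits or procedures. Tabulated counts may look slightly less favourable. Worsening in frequency can be applied only as far as the eCRF records it. Post-window SAEs are less completely ascertained than events found at scheduled visits, which is the reason for the separate table.

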4.2 Withdrawal of Patients from the Study

Patients will be followed up for 52 weeks after they enter the ABP-19002 OLE study.

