3.3. Treatments

Investigational study drug is a *Clostridium botulinum* toxin type A. Each vial contains 100 units of lyophilized ABP-450. All study patients, will be administered between 150 and 350 units of ABP-450, based on the investigator's discretion and clinical judgment.

There will be no additional retreatments after Week 48.

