3.4. Dose Adjustment/Modifications

Patients were enrolled in the ABP-19002 OLE study with the opportunity to either maintain the original Phase 2 dose or modify the dose at the investigator's discretion. As the blind will not be broken, the placebo patients (who were entered into one of the dose groups in the ABP-19000

study) can be administered any dose between 150 and 350 units of ABP-450, based on the investigator's discretion and clinical judgment. Retreatments are also based on investigator's discretion and clinical judgment.

4. General Statistical Considerations

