not be displayed to draw attention to the non-zero counts. A row denoted 'Missing' will be included in count tabulations where specified on the shells to account for missing values. The denominator for all percentages will be the number of populated patients in that treatment within the analysis set of interest, unless otherwise specified. Frequency statistics will be displayed using one decimal place except for the display of 100% frequency which will be displayed as 'XX (100)'.

- Rules for multiple assessments: To summarize data collected over time, summary tables will be presented by scheduled visit. Unscheduled visits may be included in specific summaries (such as worst post-baseline measurement) and will be described in the relevant sections. Both scheduled and unscheduled visits will be included in the data listings.
- Date and time display conventions: The following display conventions will be applied in all outputs where dates and/or times are displayed:

Date only: DDMMMYYYY

Date and time: DDMMMYYYY HH:MM

Partial dates will be listed as such (i.e., where day or day and month is missing, only MMMYYYY or YYYY will be displayed, respectively).

- Multiple comparisons: There will be no statistical adjustment for multiplicity.
- Treatment terminology and order to be used in TLF outputs:
 - Unless specified, the following labels will be used for summary tables:
 - a. ABP-450 150 units
 - b. ABP-450 250 units
 - c. ABP-450 350 units
 - For summary of disposition, demography, medical history, prior medications, and first secondary estimand, the following will be used:
 - a. ABP-450 low
 - b. ABP-450 medium
 - c. ABP-450 high

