8.1.2. Overall Summary of Adverse Events

An overall summary of TEAEs will be summarized by treatment group and treatment cycle by providing the number and percent of patients who experience the following:

An overall summary of the number and percentage of patients with at least one TEAE will be presented by SOC and PT. At each level of patient summarization, a patient is counted once if the patient reported one or more events starting in each treatment group in each treatment cycle, and across all cycles (by overall total doses of low, medium, and high). Percentages will be calculated out of the number of patients in the SAF. The table will be sorted by SOC and PT in descending order of incidence from the SOC and PT with the highest total incidence to the SOC and PT with the lowest total incidence. Summaries and listings will be presented for the SAF.

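### Adverse event percentages by treatment cycle have no common observation window, although a cycle can last 4 weeks or many months

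*SAP*

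**What the plan says.** **How events are shown.** For each dose group, SAP 8.1 gives "the number and percentage of patients experiencing an event and the number of events (based on start date of the event) by treatment cycle". Sections 8.1.2 and 8.1.4 to 8.1.10 use the same layout for the overall summary, related events, severity, serious events, events leading to treatment discontinuation or study withdrawal, SUSARs and non-serious events of special interest. Sections 8.1.2 and 8.1.6 add summaries across all cycles.

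**What sets cycle length.** SAP 4.2 restarts the study day at each cycle's injection. On timing, SAP 3.4 says: "Retreatments are also based on investigator's discretion and clinical judgment". SAP 3.3 sets the latest point: "There will be no additional retreatments after Week 48". Protocol 4.2 sets the end: "Patients will be followed up for 52 weeks after they enter the ABP-19002 OLE study". SAP 8.1 counts events as treatment-emergent "up to 5 days after the end of treatment or end of study visits".

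**Denominators.** SAP 8.1.2 states: "Percentages will be calculated out of the number of patients in the SAF". Sections 8.1.7 and 8.1.8 say the same. The general rule in SAP 4.1, which yields where another rule is given, is: "The denominator for all percentages will be the number of populated patients in that treatment within the analysis set of interest". Neither rule mentions the cycle.

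**Exposure.** SAP 7.2.1 summarises the number of patients exposed and "the cumulative number of doses and cumulative dose at each visit within each treatment cycle". It covers doses and units, not weeks observed.

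**The concern.** The primary objective is the safety of repeat injections. The by-cycle tables are the readable outputs that show whether adverse events change from one injection to the next. Their columns rest on unequal observation. A patient injected at Week 48 contributes about 4 weeks to that cycle, while a patient not injected again after Week 20 contributes 32 weeks to theirs. With crude percentages and counts, a steady risk can appear to fall or rise, and a real change can be hidden. Dose groups within a cycle are exposed to the same problem if retreatment timing differs by dose.

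The denominator is a second problem. If late-cycle percentages are divided by everyone in the Safety Analysis Set, patients who never reached that cycle count as event-free.

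**Working it through.** The plan states no event rate, onset time or power calculation for this point, so there is no planned figure to reproduce. Event risks, onset times and injection spacings below are assumptions for illustration.

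**1. Length of the last cycle.** A cycle is taken to run from one injection to the next, or to study exit. That is an inference from the study-day rule in SAP 4.2, since the readable text does not say when a cycle ends.
- Shortest: 52 − 48 = 4 weeks, or 28 + 5 = 33 days to the treatment-emergent cut-off.
- Even spacing of 8, 12 or 16 weeks with an injection at Week 48: 4 weeks.
- Even spacing of 14 weeks (last at Week 42): 10 weeks. Even spacing of 10 weeks (last at Week 40): 12 weeks.
- Last injection at Week 36: 16 weeks. At Week 20: 32 weeks.

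**2. Constant hazard.** Risk over w weeks = 1 − (1 − p)^(w/12), where p is the 12-week risk. With p = 20%:

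| Weeks observed | Percentage shown |
|---|---|
| 4 | 1 − 0.80^(1/3) = 7.2% |
| 33 days | 1 − 0.80^(33/84) = 8.4% |
| 12 | 20.0% |
| 16 | 25.7% |
| 32 | 44.8% |

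For 12-week risks of 10%, 30% and 40%, the 4-week figures are 3.5%, 11.2% and 15.7%.

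**3. Early onset.** With exponential onset of mean m weeks, the share of the 12-week risk seen in 4 weeks is (1 − e^(−4/m)) / (1 − e^(−12/m)). For m = 1, 2, 3 and 4 this is 98%, 87%, 75% and 67%, so 20% shows as 19.6%, 17.3%, 15.0% and 13.3%. If every event starts within 4 weeks, the table shows 20% and there is no distortion. Long cycles inflate little here: at m = 4, 32 weeks shows 20% × (1 − e^(−8)) / (1 − e^(−3)) = 21.0%.

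**4. Mixed columns.** Tables are by cycle number, so one column can hold short and full cycles. If half the patients have 4 weeks and half have 12, at constant hazard the column shows 0.5 × 7.2 + 0.5 × 20 = 13.6%.

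**5. Denominator.** SAP 4.3 expects about 59 patients. If 30 reach a late cycle (assumed) and 20% of them have an event, that is 6 patients. Out of 30 it is 20%; out of 59 it is 10.2%.

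**6. Does a rate per patient-week solve it?** At constant hazard, yes: −ln(0.80)/(12/52) and −ln(0.80^(1/3))/(4/52) both give 0.97 first events per patient-year. If all of a 20% risk falls in the first 4 weeks, no: 0.20/4 = 0.050 per patient-week in a 4-week cycle against 0.20/12 = 0.017 in a 12-week cycle. The short cycle then looks three times as hazardous.

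**7. Does a 28-day window fit?** With the injection as Study Day 1, an injection at Week 48 and exit at Week 52, days 1-28 fall within planned follow-up.

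**The case against.** The strongest reply is that these tables are descriptive. SAP 4.3 says no comparative analyses are planned, and all adverse events are listed. That stands, and no formal test is at risk. But adjacent cycle columns invite comparison, and descriptive figures also need a common basis.

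Several stronger readings are tempting, and the documents do not support them:
- *A reader might infer that later injections will look safer because they are watched for less time.* The direction is not fixed. Last cycles can also be long, which pushes percentages up, and early onset leaves little distortion. Patients who reach later cycles are also a selected group, so observation time would not be the only explanation for a fall.
- *A reader might infer an apparent fall of about 64% (1 − 7.2/20).* That needs constant hazard and every patient in the column having exactly 4 weeks. It is a worst case on assumed inputs.
- *A reader might infer that the primary result is biased.* Protocol 7.5.1 describes the proportion of patients with treatment-related serious events up to Week 52 in the retreated set. It is cumulative, not by cycle.

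Parts of SAP 8.1 to 8.1.2, the visit schedule and the retreatment text are redacted or not shown. A minimum interval or an exposure-adjusted table may exist there, so the point is limited to the readable text.

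**Conclusion.** The point holds in limited form. By-cycle percentages and counts in the readable SAP can be distorted by unequal observation, in either direction. On an assumed 20% risk per 12 weeks, a 4-week cycle shows between 7.2% (constant hazard) and 20% (all events early), and a 32-week cycle shows up to 44.8% (constant hazard). Actual size and direction depend on onset times and retreatment intervals that the documents do not give. The denominator wording in SAP 8.1.2, 8.1.7 and 8.1.8 could add to this: in the illustration it halves a late-cycle figure, from 20% to 10.2%, if it is not limited to patients dosed in that cycle. This is an inexpensive improvement to descriptive tables and does not call the primary analysis into question.

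**What to change.** In SAP 8.1 and the by-cycle tables for adverse events, serious adverse events and events of special interest:

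1. Add incidence with onset in days 1-28 after each injection. The denominator should be patients injected in that cycle and, where split, that dose group. Base any statement about the pattern across cycles on this.
2. State in 8.1.2, 8.1.7 and 8.1.8 whether by-cycle percentages use patients dosed in that cycle or the whole Safety Analysis Set.
3. Report weeks observed per cycle and event rates per patient-week as supportive only, because the rate overstates short cycles when events cluster early.
4. Keep the crude percentages and counts, labelled as descriptive.

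The cost is SAP wording and extra columns, since injection dates and event onset are already collected. The 28-day window leaves out later-onset events, but these remain in the crude tables and listings. If an unreadable part of the SAP already contains such a table, only the denominator wording needs attention.
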